Antibody responses: We will analyze the breadth and magnitude of antibody responses by assessing PPSV23/PCV13 serotype-specific IgG titers at day 0 and 28, as recommended by the World Health Organization, and using the Opsonophagocytic assay. This assay (serotypes 4, 6B, 14 and 23F) will be performed using serotype-specific *S.pneumoniae* incubated with serial-diluted heat-inactivated sera [3]. Newborn rabbit serum is added as a source of complement and differentiated HL-60 cells are added. Sera are tested in duplicate and results obtained using the Opsotiter 1 software. We will use U-scores to rank antibody response by titer, affinity and number of serotypes (as done for antigen-specific T cells in response to DC vaccines [4-6]. Our collaborator, [name], will assess serotype-specific anti-polysaccharide responses. His lab will also measure antibody avidity and opsonizing capacity as described [7].

CMV status. Influenza vaccine studies in the elderly have revealed a critical role for CMV status [8]. In a single study, CMV status did not appear to influence antibody responses to PPSV23 vaccine in older adults, yet its role in other aspects of immune responses or in baseline pre-vaccination status cannot be ruled out[9]. As a result, we will obtain CMV status using antibody titers and PCR-based technologies [10], and will include this variable in our analytic plan.

Analytical Approaches:

1. *Multicolor flow cytometry*: 0.5 ml of blood will be used to determine the profile of circulating immune cells. We designed five multi-color monoclonal antibody cocktails that will permit us to establish the detailed phenotype of T-cell subsets, monocytes, DCs and B-cell subsets. We included a set of antibodies to identify NKT cells, as these cells have been reported to contribute to responses to PPSV23 vaccination [11].

2. *Cryopreservation of isolated PBMCs and sorting of purified populations*: We have validated monoclonal antibody cocktails that permit us to sort T-cell subsets, monocytes, DCs and B cells for cryopreservation (**Table 1**). PBMCs will be frozen in 4–5 aliquots (recovering on average 20×10^6 cells); 1–2 will be used for ATAC-seq and 2–3 for functional studies. After thawing we will sort monocytes, CD1cDCs, CD45RO+CD4+ T cells, and B cells for ATAC-seq and RNA-seq. We aim to collect 15,000–25,000 of each type of cells.

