To investigate our hypothesis we will apply RNA-seq, rather than DNA microarrays, to generate transcriptional profiles, as this will enable quantitative assessment of both coding RNAs and ncRNAs. We will also use ATAC-seq to resolve the epigenetic landscape of immune cells in healthy elderly in the context of vaccine responses.

Approach:

1. *Blood transcriptomics by RNA-seq:* We will carry out RNA-seq of whole blood samples at baseline, day 1 and day 10. Samples collected from days 28 and 60 will be kept frozen for future studies. RNA-seq on purified cell subsets will be performed using purified cells from the five lowest and five highest responders for each vaccine. Sequencing will be performed at JAX-GM with an Illumina HiSeq2500.
2. *Blood epigenomics analysis by ATAC-seq:* We will analyze PBMCs, CD4+ T cells, monocytes, CD1cDCs and B cells (25×10^3 cells per assay). We are also developing assays with lower cell numbers to address the scarcity of some populations, and are encouraged by reports of single cell ATAC-seq [17]. We will generate a database describing the DNA accessibility landscape of major immune-cell subsets from elderly individuals at steady state. The data will also include the DNA accessibility landscape of monocytes, T and B cells analyzed at different time points following vaccination with the two pneumococcal vaccines. For these in-depth studies, we will select the five highest and five lowest responders for each vaccine.

Correlative analysis: We will correlate the increased levels of day 28 anti-pneumococcal antibodies as defined in Aim 1 with all the parameters collected in this aim. Parameters include: 1) cellular composition at baseline, day 1 and day 10 post-vaccination; 2) transcriptome analysis on blood and purified immune cell subsets at baseline, day 1 and day 10; 3) ATAC-seq data on PBMCs and purified cell subsets at the different time points and 4) pneumococcal colonization at baseline and at day 28. A detailed description of the statistical approaches is given below (see Integrative Data Analysis section).

1.3 Specific Aim 3

To examine the functional status of immune cells in the elderly stratified according to their pneumococcal vaccine responder status.

Hypothesis: We hypothesize that lack of *in vivo* response to PPSV23 and PCV13 depends on alterations to APCs, Tfh cells or B cells.

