8 INTEGRATIVE DATA ANALYSIS

8.1 Statistical Methods

The breadth and magnitude of IgG titers will be analyzed individually and together using best-response and multivariate U-statistic approaches [4, 97]. Differences among groups (e.g., responder status) and/or time of immunological variables (e.g., flow, RNAseq) will be assessed using generalized linear mixed-model analyses with appropriate distributional assumptions (e.g., normal, negative binomial) and link functions (e.g., identity, log). Propensity scores [98] will be adjusted for possible confounds such as gender, age, race and ethnicity, while the Bonferroni correction or Benjamini and Hochberg false discovery rate (FDR) will account for multiple testing [99]. Correlation of clinical and immunological variables will be conducted using the Pearson or Spearman Correlation Coefficient depending on whether or not the assumptions of linearity and homoscedasticity are met. For class prediction, a variety of methods including k-nearest neighbors, radial basis machine, random forests, boosted trees and support vector machines will be employed and validated using leave-one-out cross-validation. Unsupervised analysis of high dimensional data will be conducted using heatmaps, hierarchical cluster analysis and principal component analysis. Lastly, attrition and missing data are issues in longitudinal [100] and elderly studies [101]. "Missingness" will be characterized and multiple imputation applied when appropriate [102-104]. Drs. [name] (JAX) and [name] (SIDRA) will assist with statistics and bioinformatics as needed.

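### Pearson or Spearman coefficients computed only in the five highest and five lowest responders do not estimate the whole-arm correlation with the day 28 antibody rise, and Section 8.1 does not allow for this (minor)

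*Combined protocol and SAP*

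**What the plan says.** Section 1.2 restricts the sorted-cell work: "RNA-seq on purified cell subsets will be performed using purified cells from the five lowest and five highest responders for each vaccine". For ATAC-seq it says: "For these in-depth studies, we will select the five highest and five lowest responders for each vaccine". How much of the ATAC-seq this covers is not fully spelled out. The opening of Section 1, which places transcriptome and epigenetic work in selected high responders and non-responders, and the remark in Section 2.1 that frozen samples allow ATAC-seq to be run once responses are known, both favour the restricted reading.

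The correlative analysis in Section 1.2 then states: "We will correlate the increased levels of day 28 anti-pneumococcal antibodies as defined in Aim 1 with all the parameters collected in this aim". Its list includes "transcriptome analysis on blood and purified immune cell subsets at baseline, day 1 and day 10" and ATAC-seq on PBMCs and purified subsets, next to cellular composition. It refers to the Integrative Data Analysis section for methods. There, Section 8.1 says: "Correlation of clinical and immunological variables will be conducted using the Pearson or Spearman Correlation Coefficient", with the choice resting on linearity and homoscedasticity. Multiple imputation is raised for attrition and missing data, not for participants left unassayed by design.

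On the ranking variable, Section 1.1 says: "We will use U-scores to rank antibody response by titer, affinity and number of serotypes". Section 8.1 says: "The breadth and magnitude of IgG titers will be analyzed individually and together using best-response and multivariate U-statistic approaches". Neither states which variable picks the five and five, or how closely it follows the day 28 rise.

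**The concern.** Keeping the extremes of a variable and dropping the middle enlarges its variance, and a non-zero correlation with that variable grows as a result. Here the participants are chosen on antibody response and the marker is then correlated with antibody response. A sorted-cell coefficient could therefore look stronger than a coefficient of equal true strength from an assay run on the whole arm, because of sampling alone. Aim 2 is about profiles linked with antibody response, so the strength of association is one of its outputs.

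The ranking score also contains affinity and number of serotypes. A marker related to one of those is selected partly through a route other than the correlated antibody measure, which can move its coefficient in a different way.

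**Working it through.** **Inputs.** From the documents: 20 per arm (Sections 3 and 8.2), five highest and five lowest per vaccine (Section 1.2), Pearson or Spearman (Section 8.1). The plan gives no figure for these correlations; its power figure in Section 8.2 concerns differential expression and has no bearing here. Assumed, because the documents do not give them: bivariate normality, the true correlation ρ, and the correlation between ranking variable and antibody measure (the link), taken as 1.0, 0.8 and 0.5.

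**Step 1, closed form at link 1.0.** Let k be the mean square of the antibody measure in the selected ten, in units of its variance in the arm. For the top and bottom five of 20, k = 1.78. Then

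r(selected) ≈ ρ√k / √(1 + ρ²(k − 1)).

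- ρ = 0.3: 0.3 × 1.335 / √(1 + 0.09 × 0.78) = 0.400 / 1.035 = 0.387.
- ρ = 0.5: 0.5 × 1.335 / √(1 + 0.25 × 0.78) = 0.667 / 1.093 = 0.610.

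**Step 2, simulation (40,000 arms per setting).** A is the antibody measure, U = link × A + noise ranks the participants, and M = ρA + noise is the marker. Mean coefficient between A and M:

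| | Pearson, true 0.3 | Pearson, true 0.5 | Spearman, true 0.3 | Spearman, true 0.5 |
|---|---|---|---|---|
| Selected ten, link 1.0 | 0.39 | 0.61 | 0.36 | 0.58 |
| Selected ten, link 0.8 | 0.36 | 0.57 | 0.34 | 0.54 |
| Selected ten, link 0.5 | 0.31 | 0.52 | 0.29 | 0.48 |
| All 20 | 0.29 | 0.49 | 0.27 | 0.46 |

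The population Spearman values are 0.29 and 0.48, so at link 0.5 Spearman does not overstate them. The SD of one Pearson r in ten people is about 0.29 at true 0.3 and 0.21 to 0.25 at true 0.5. At true 0 the mean is 0.00 and the rejection rate about 0.05.

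**Step 3, marker also tied to another part of the score.** Add to M an effect of the part of U that A does not explain (links 0.8 and 0.5).

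- True 0, extra effect 0.3: mean r about 0.10, rejection 0.055 to 0.059.
- True 0.3, extra effect 0.2 to 0.3: mean r 0.37 to 0.44.
- True 0.3, extra effect −0.2: mean r 0.29 (link 0.8) and 0.25 (link 0.5).

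The direction is therefore not fixed, and the null behaviour in Step 2 holds only when the marker relates to the score solely through the correlated antibody measure.

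**Step 4, what repairs it.**

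- The slope of M on U in the ten is unbiased under linearity: 0.301, 0.244 and 0.152 against true 0.300, 0.240 and 0.150 (ρ = 0.3, links 1.0, 0.8, 0.5), with 95% interval coverage of 0.949 to 0.950.
- When ranking and correlated variable are the same, r·u / √(1 + r²(u² − 1)), with u the ratio of the SD in all 20 to that in the ten, gives 0.31 for a true 0.3 and 0.51 for a true 0.5.
- When they differ, a range-corrected r with U is another quantity: 0.25 and 0.16 at links 0.8 and 0.5, where the correlation with the antibody measure is 0.3.
- In that case regress M on A and U in the ten to get coefficients b and a residual variance s². With S the covariance matrix of (A, U) in all 20, the covariance of A and M is the first element of Sb, the variance of M is b′Sb + s², and r follows. This recovers the planned correlation to within about 0.04 in every setting run.

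**The case against.** Sampling the extremes is a legitimate, economical design for detection, and Section 1.2 states the selection openly. Section 8.1 already plans group comparisons: "Differences among groups (e.g., responder status) and/or time of immunological variables (e.g., flow, RNAseq) will be assessed using generalized linear mixed-model analyses". It also plans Bonferroni or false discovery rate control. The study is exploratory, the shift is small beside the noise of one coefficient in ten people, and no section says that coefficients will be ranked across assays or presented as cohort-wide estimates. Nor does Section 1.2 say outright that whole-blood RNA-seq covers all 20 in each arm; Section 8.2 suggests it, while the opening of Section 1 could be read the other way. A larger distortion comes from reporting only significant markers: at true 0.3 and link 1.0, those with p<0.05 average |r| 0.73, and still 0.62 after range correction (0.55 in all 20).

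Most of this stands, and it is why the point is minor. It does not remove the point, because the shift is systematic across truly associated markers, does not average out, and goes unmentioned in the plan.

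A reader might infer that the selection fills the results with false positives, or that it always enlarges the coefficient. The documents support neither. Under the simple model the null test keeps its level, the departure in Step 3 is slight, and a negative link to another score component can shrink r.

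**Conclusion.** The concern holds in a limited form. For sorted-cell RNA-seq, and for whatever ATAC-seq is confined to the five and five, a plain Pearson or Spearman coefficient does not estimate the whole-arm correlation with the day 28 rise. If the ranking variable is the correlated measure, the mean Pearson excess over all 20 is about 0.09 at true 0.3 and 0.12 at true 0.5. At an assumed link of 0.5 it is 0.02 and 0.03. With a second route from marker to score, the sign is open. These sizes rest on bivariate normality and on links and extra effects that the documents do not give.

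It would go too far to conclude that the extreme-group design is wrong, that all Aim 2 correlations are affected, or that the responder-status models are distorted. Those models describe the groups actually sampled, and nothing here touches assays run on everyone. Severity: minor.

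**What to change.** In Section 8.1, for assays run only on the five and five:

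- Make the already planned high-versus-low contrast the reported effect measure, or the within-vaccine slope on the ranking variable with its confidence interval.
- If a correlation with the day 28 rise is also reported, choose one of two routes. Either rank responders by that same rise and apply the range correction with its SD in the whole arm, or correct with both the ranking score and the antibody rise, which are known in all 20, as in the last item of Step 4.
- Do not present a corrected r with the ranking score as the correlation with the day 28 rise.
- Label any uncorrected Pearson or Spearman coefficient as coming from an extreme-group sample, and do not compare it with whole-arm coefficients.
- Name the variable that ranks responders.

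In Section 1.2, one sentence should say which ATAC-seq data are confined to the five and five. Pearson or Spearman can stay for data measured on everyone.

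The cost is a paragraph, a sentence and a few lines of programming on the same data. The downsides are slopes in marker-specific units and reliance on linearity, which is hard to check without the middle ten. The correction also does not remove the inflation from reporting only significant markers, and the text should say so.

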2 BACKGROUND, RATIONALE AND SIGNIFICANCE

2.1 Background and rationale

Aging, pneumococcal vaccines and *S. pneumoniae* infection: The declining ability of the aging immune system to combat infection is a major threat to the health, independence and survival of older adults [36-39]. Cellular immunosenescence associated with a hyper-inflammatory state has been linked to many diseases common in the elderly, including infectious diseases [36, 40, 41]. Beyond evidence of poor immune-cell responses with declines in naïve T cells, we know little about the mechanisms of immunosenescence [41-43].

Pneumococcus infection is one common condition in the elderly for which a better understanding of immunosenescence and immune responses to vaccines is urgently needed [8, 44-50]. The polysaccharide pneumococcal vaccine PPSV23 has long remained the only vaccine recommended for prevention of pneumococcal infection in healthy adults >65 and children and adults 2 to 64 years of age with certain health conditions. However, its efficacy was felt to be poor, especially against non-bacteremic pneumonia and in advanced age. Although young and old subjects might demonstrate similar increases in antibody levels post-PPSV23 immunization, the functional activity of these antibodies is lower in the elderly. In contrast, the 13-valent pneumococcal conjugate PCV13 has superior immunogenicity against some serotypes. The CAPiTA trial [51], a randomized placebo-controlled trial of PCV13 involving nearly 85,000 Dutch individuals ≥65 years, indicates that PCV13 has 75% efficacy against invasive pneumococcal infections caused by PCV13 serotypes and 45% efficacy against non-bacteremic variants. In contrast, evaluation of a national program of PPSV23 vaccination in Taiwan [52] in individuals 75 years and older revealed that vaccination in the previous year was associated with a 60% reduction in pneumonia hospitalization, a 76% reduction in invasive pneumococcal disease and >90% reduction in related death in this vulnerable population. In spite of these striking findings, no definitive conclusions can be drawn with regards to the comparative efficacy of the two vaccines, since in both studies PCV13 or PPSV23 were each compared to placebo and not each other. The 2015 CDC Guidelines recommend, for healthy older adults (≥ 65 years) who have not received a pneumococcal vaccine, that PCV13 be administered first followed by PPSV23 ≥ 1 year later, and for those that have received PPSV23, a dose of PCV13 ≥ 1 year later [53]. Thus, the two vaccines may remain complementary to each other, with benefits dependent on which serotypes are most responsible for community-acquired pneumonia in a given population, but many questions as to the nature of (and variability in) vaccine responsiveness remain unanswered.

Even within the landscape of broad late-life vulnerability to infectious diseases, pneumococcal infection assumes an overwhelmingly important role [54]. Thus, preventive strategies such as vaccination remain crucial. It is known that T- and B-cell receptor repertoires become more skewed during aging, and likely contribute to the limited specific immune responses to vaccines or new infections [44]. However, we lack fundamental insight into the transcriptional and epigenetic signatures that could be predictive of immunosenescence and reduced vaccine responsiveness at the personalized level—and could enable us to identify and target individuals most at risk of complications from poor responsiveness to pneumococcal and potentially other vaccines.

Immune responses to vaccination are complex and depend on the coordinated actions of specific B- and T-cell subpopulations. B-cell responses are classified as T-cell-dependent (TD) or T-cell-independent (TI) based on the requirement for T-cell help in antibody production [55]. TD antigens are processed then presented by MHC class-II molecules for recognition by cognate helper T cells. Mouse studies show that B1 cells and splenic marginal zone B cells play major roles in the TI response [56]. In contrast, the human counterpart of mouse B1 cells, the IgM+ memory B cells, remains the object of some controversy [57-61].

Several studies have identified the importance of pneumococcal polysaccharide (PS)-IgM antibodies in generating protective immunity against *S. pneumoniae* [62]. These antibodies are in part produced by human IgM memory B cells [7, 32, 33]. This population of IgM+ memory B cells is reduced in the elderly, splenectomized persons, infants less than two years of age and a subgroup of Common variable-immunodeficiency patients—all of whom respond poorly to PS vaccines and are susceptible to infections with encapsulated microbes [63]. These findings support the concept that IgM+ memory B cells are important in generating responses to TI antigens. It is however unlikely that IgM+ memory B cells are solely responsible for anti-PS antibody production. Indeed, switched memory B cells (CD27+IgM-) secrete higher levels of anti-PS antibody than CD27+IgM+ memory cells following *in vitro* stimulation. This might be due to additional PS-responsive B-cell subsets and/or the versatile role that IgM memory cells play in pneumococcal antibody responses.

Follicular helper T cells (Tfh) play a critical role in the generation of high-affinity memory B cells [12, 64-69]. The memory Tfh cell compartment in human blood is composed of subsets that differentially express the chemokine receptors CXCR3 and CCR6 and display different functions [67]. Recently, we demonstrated a direct correlation between activation of Flu antigen-specific Tfh1 responses and the generation of antibody responses upon vaccination [12](see Preliminary Studies). However, how Tfh cells regulate antibody responses to pneumococcal vaccines in elderly is unknown.

Systems biology of immunity and vaccine responsiveness in humans: We [70] and others [71-76] used systems biology approaches to investigate immune responses to vaccines. We found that young adults mount distinct responses to Flu (Fluzone®) and pneumococcal (PPSV23) vaccines (see Preliminary Studies). Our results provide proof-of-principle that we can detect global immune responses elicited by different vaccines and suggest that comparative analyses of these differences will be critical for understanding the immune mechanisms underpinning successful vaccination. Here, we propose to apply these and other novel immunogenomic approaches to further understand how protective immunity against pneumococcal antigens is established in healthy elderly using two pneumococcal vaccines.

PRELIMINARY STUDIES

I) IMMUNOGENOMICS OF PNEUMOCOCCAL VACCINATION.

Different vaccines elicit distinct transcriptional profiles in blood cells. To investigate the innate and adaptive immune responses to Flu (Fluzone®) and pneumococcal (PPSV23) vaccines, we performed transcriptional profiling of whole blood using DNA microarrays. These studies revealed significant differences in the quality and magnitude of transcriptional responses at different time points after each vaccination. Specifically, we found that influenza vaccination elicited type-I interferon signaling signatures, while PPSV23 vaccination was associated with an acute inflammatory response signature linked with myeloid cells. The day 7 plasmablast response

induced by both vaccines was more pronounced after PPSV23 vaccination. These findings provide proof-of-principle that a transcriptomics approach can be used to identify distinct global immune responses elicited by different vaccines.

Decoding innate responses to PPSV23 vaccine in vitro. In an effort to decipher the mechanisms leading to blood signatures *in vivo*, we assessed the transcriptional profiles of various antigen-presenting cells (APCs) exposed to vaccines *in vitro* [77]. Monocytes, *in vitro*-derived IL-4 dendritic cells (DCs), blood CD1c+ DCs and CD141+ DCs from 4–5 donors were stimulated with vaccines for six hours. Their transcriptional fingerprints yielded 23,060 transcripts. A modular analysis, initially developed to characterize the blood transcriptome [78-81], identified 42 differentially expressed modules, forming four groups of transcriptionally active conditions. We then analyzed 22 modules induced by Fluzone®, PPSV23 or human papilloma virus (HPV) vaccine in IL-4 DCs, monocytes or CD1c+ DCs. Importantly for the proposed studies, PPSV23 induced unique modular signatures in monocytes, including IL-1, NF κ B and type II IFN-related modules. We will further develop these analyses and determine the mechanisms underlying differential responses of APCs to PPSV23 and PCV13. APCs from elderly individuals, responding or not to PPSV23 or PCV13, will be compared to determine whether non-responsiveness can be linked with specific APC alterations.

II) ADAPTIVE IMMUNE RESPONSES TO VACCINATION. To begin to define the cell types that comprise adaptive immune responses to vaccination, we performed detailed phenotypic analyses of T-cell subsets taken from healthy young adults vaccinated or not with Flu or PPSV23 vaccine. We found that vaccination induced ICOS expression almost exclusively on blood CXCR3⁺ Tfh cells and that the induced ICOS⁺CXCR3⁺ Tfh cell population was enriched with cells specific for Flu antigens. The increase in ICOS⁺CXCR3⁺ Tfh cells in blood at day seven post-vaccination correlated with an increase in antibody titers at Day 28. Isolated ICOS⁺CXCR3⁺ Tfh cells induced antigen-loaded memory B cells to produce Flu-specific Abs *in vitro* through secretion of IL-10 and IL-21. Thus, the analysis of blood Tfh subsets led us to discover biomarkers reflecting vaccine efficacy and provided insights into vaccine mode of action. Further studies in healthy young adults vaccinated with PPSV23 indicated 1) a plasmablast response on days 7 and 10 and 2) the emergence of ICOS⁺ Tfh cells in blood peaking at day 10. However, the status of Tfh cells in elderly has not been well characterized. We will address this gap by profiling the Tfh cells of healthy elderly vaccinated with either PPSV23 or PCV13.

III) IMMUNOGENOMICS OF BLOOD CELLS FROM OLDER ADULTS. We recently launched a systematic analysis of the status of immune cells in the blood of elderly subjects (age 65 and older; mean=75.3 yrs). Our approach included 1) assessment of cell composition by polychromatic flow cytometry; 2) transcriptional profiling by RNA-seq and 3) assessment of epigenetic landscape of PBMCs as well as sorted subsets by ATAC-seq (Assay for Transposase Accessible Chromatin or ATAC-Seq)[82]. ATAC-seq captures open (i.e., transcriptionally active) chromatin sites and can be used to reveal various categories of epigenetic information, including the genomic locations of open and closed chromatin regions and their interplay with DNA-binding proteins, as well as of individual nucleosomes. Importantly, ATAC-seq generates information *via* a simple two-step protocol that requires only a few thousand cells, making it uniquely suited to study epigenomic profiles of human clinical samples with a systems biology approach, where small cell numbers are a limiting factor.

Reproducibility of ATAC-seq datasets: To determine the feasibility of ATAC-seq for studying the epigenome of immune cells in the elderly, we conducted a pilot study in PBMCs (50,000 cells per experiment) of ten healthy young (20–30 yrs) and ten healthy old (>65 yrs) individuals. Each sample was run in triplicate to confirm reproducibility. ATAC-seq datasets were also generated in FACS-sorted B cells and in naïve and memory CD4+ and CD8+ T cells. We identified ATAC-seq peaks, i.e., open chromatin sites, in each of these PBMC samples. First, we confirmed that our identified ATAC-seq peaks are consistent with PBMC histone modification mark profiles generated by the Roadmap consortium, where ATAC-seq peaks are enriched in active marks (H3K9ac, H3K36me3, H3K4me1) and depleted in inactive marks (H3K9me3 and H3K27me3) (data not shown). Next, we calculated pairwise correlations between ATAC-seq datasets based on read count distribution across the whole genome and clustered the resulting correlation matrix (using hierarchical clustering algorithm) to identify similarities between ATAC-seq datasets globally.

Our analyses showed that ATAC-seq datasets are reproducible and capture cell-type-specific epigenetic landscapes. We found a good match between observed and expected open chromatin sites around cell-type-specific genes, e.g., the CD14 gene promoter had an open chromatin site in CD14+ monocytes (data not shown). We also identified cell-type-specific open chromatin sites in CD4+ and CD8+ cells by comparing memory and naïve ATAC-seq samples. We found that cell-type-specific open sites lose their specificity with aging both in CD4 and CD8 cells, with the change being more dramatic in CD8+ T cells. This preliminary study confirms that our ATAC-seq data generation and analysis workflow yields highly reproducible and high-quality ATAC-seq datasets from PBMCs and sorted cell populations.

ATAC-seq identifies age-associated epigenetic changes in open chromatin sites: In our next set of ATAC-seq analyses, we sought to identify open chromatin sites remodeled with aging in PBMCs, i.e., open chromatin sites closing with age (“young specific”) or relatively closed chromatin sites opening with age (“old specific”). To do this we used an algorithm designed to capture differential sites from read count data based on negative binomial distributions; this allowed us to capture a total of ~20,000 differentially open chromatin sites (at 0.05 FDR cut-off, out of 100,000 consensus ATAC-seq peaks) between age groups, where ~11,000 were young specific and ~9000 old specific.

Among these differential sites, we found a remarkable genomic distribution bias between old-specific and young-specific open chromatin sites, whereby young-specific sites were mostly at promoters, whereas old-specific sites were enriched in intergenic and intronic regions. We confirmed that these differentially open chromatin sites separate age groups (i.e., elderly and young PBMCs) using the first two components of a principal component analysis (PCA) (data not shown). Among these differential open chromatin sites, we were further intrigued to find age-dependent closure of chromatin sites at the IL-7R promoter. This decline in chromatin accessibility correlated with a significant decrease in IL7R expression, as measured by RNA-seq. We also confirmed by flow cytometry that IL7R expression is decreased in elderly CD8+ T cells (data not shown). Moreover, among our “young-specific” differentially open chromatin sites, we identified ~60 promoter and intergenic ATAC-seq peaks targeting other genes in the IL7 signaling pathway, which is in agreement with the literature, as alterations in lymphocyte homeostasis related to the IL7/IL7R pathway have been reported in old mice and humans [83-87]. These analyses reveal that the epigenome of the IL7R signaling pathway significantly closes with aging, thereby

uncovering a putative mechanism to explain the decreased ability of elderly individuals to deal with new antigenic challenges. They also further validate our approach using ATAC-seq to identify age-dependent differences in the epigenomes of healthy individuals. Here, we will extend these findings to determine whether vaccine responders and non-responders show differential expression and differential epigenetic profiles of immune-related molecular pathways. We will also analyze whether responders, in contrast to non-responders, reactivate their IL-7R pathways.

Modular interpretation of age-associated epigenetic changes. To systematically interpret the biological meaning of the remodeled open chromatin sites identified via ATAC-seq, we employed the transcriptional immune module analysis described in Fig. 1B, composed of gene sets that are coordinately expressed in PBMCs in a wide range of diseases (28 modules in total from 239 microarray profiles) [79-81, 88]. We developed and used this stable modular framework extensively to interpret immune signatures associated with diverse diseases and immune responses. We first identified putative (i.e., nearest) gene targets for ATAC-seq open chromatin sites. For each module, we then calculated the average log-fold change of read counts per gene between old and young samples for genes imputed to differential open chromatin sites. We next isolated modules whose chromatin landscape significantly changes with age, identifying 12 modules that are differentially open in samples from young individuals, including a module of T-cell regulators, and five modules that are differentially open in samples from elderly, including modules associated with neutrophil and platelet function and inflammation. We also investigated whether we can capture differences in module profiles of individual epigenomes when compared to population averages (i.e., all samples).

We observed systematic and distinct differences in the relative openness of certain modules in samples from elderly versus young individuals, e.g., neutrophils vs. T-cell modules, which helps us to interpret the regulatory implications of epigenetic changes. Module-based functional analysis revealed that i) young-specific open chromatin sites mostly occur around promoters and are associated with modules related to T cell functions and ribosomal proteins; and ii) old-specific open chromatin sites mostly occur at intronic/intergenic sites and are associated with modules related to inflammation and neutrophil and platelet activity. Our modular analyses also helped us to identify outlier samples, including an old individual with a chromatin profile similar to samples from young individuals and vice versa. Modular analysis of immune epigenomes thus reinforced and enhanced our ATAC-seq analyses to provide greater insights into the immunogenomic profiles of elderly individuals. Here, it will be used to interpret epigenetic remodeling changes induced by vaccination in the elderly and to study whether responders and non-responders have different modular profiles before and after vaccination.

ATAC-seq datasets can be obtained from frozen samples. We next performed ATAC-seq on fresh and cryopreserved PBMCs from two different individuals. Our analyses revealed that fresh and frozen samples yield very similar genome-wide read-count profiles (data not shown), with only 44 peaks out of 75,365 total consensus open chromatin sites being different. These results confirm that ATAC-seq profiles can be obtained from frozen samples. This will enable us to retrospectively generate ATAC-seq datasets after vaccination responses are quantified, thereby significantly reducing experimental costs.

Differentially expressed non-coding RNAs in aging. Aging is associated with a complex transcriptional signature that includes changes to ncRNA profiles in addition to coding genes [89-96]. ncRNAs include small transcripts such as microRNAs and lncRNAs [1]. Although many

ncRNAs have been identified, only a few have been fully characterized in terms of their regulatory roles in important cellular processes, including aging. To determine whether ncRNAs are remodeled in elderly human blood, we used limma software to identify differentially expressed ncRNAs between old (n=8) and young (n=10) RNA-seq PBMC samples ($p < 0.05$). This analysis revealed 24 ncRNAs differentially expressed in aging. We will expand our preliminary datasets and analyses to analyze the expression of ncRNAs in aging and determine their relationship to the vaccine response status.

